## 4.2 Simultaneous Spectacles and Patching

Participants randomized to the simultaneous group will be treated simultaneously with a spectacle correction worn all waking hours (spectacles confirmed at the Spectacle Baseline / Randomization Visit and in accordance with the criteria in *section 2.3*) and patching of the non-amblyopic eye for 2 hours per day / 7 days per week.

- Adherence with spectacle wear will be monitored throughout the study by a parental calendar.
- Adherence with patching will be monitored throughout the study by an occlusion dose monitor
- 593 (ODM) worn on the inside of the patch.

- Participants will continue their treatment and return for scheduled follow-up visits until no further improvement or worsening ("stable/worsening") of VA is reached (see *section 4.3* below) or 56 weeks.

  If no further improvement or worsening ("stable/worsening") of VA, but the participant has
- If no further improvement or worsening ("stable/worsening") of VA, but the participant has residual amblyopia ("stable residual"), treatment will be at investigator discretion but participants will continue 8-weekly visits until 56 weeks.

If non-improvement ("stable/worsening") is reached AND amblyopia is no longer present (less than or equal to 1 logMAR line) (meeting the definition for "stable resolved", *section 4.3.5*), participants will continue spectacle wear only (i.e. discontinue patching) and 8-weekly visits until 56 weeks.

In participants who meet the definition of stable resolved, but amblyopia recurs (defined as a 2 or more logMAR line decrease in VA from the level measured at the visit when the definition of "stable resolved" was last met) prior to the 56-week visit, they will be treated and the method of treatment will be at investigator discretion.

## 4.3 Amblyopia Status

- At each follow up visit, the website will determine if a participant is no longer demonstrating
- 614 improvement of visual acuity ("stable/worsening"). If a participant is no longer improving in
- visual acuity ("stable/worsening"), amblyopia status will then be defined as residual or resolved
- to direct the next step in randomized treatment, as described in 4.1 and 4.2. The subsections
- below provide the study definitions of VA improvement, VA non-improvement
- 618 ("stable/worsening"), and the criteria for determining amblyopia status (residual, resolved,
- 619 recurrent).

606 607

608

609

610

611 612

627 628

634

637

## 620 **4.3.1 Improvement of Visual Acuity**

- 621 Improvement of VA is defined as an improvement in distance VA of 0.05 logMAR or more, (VA
- 622 is calculated as the mean of test and retest at each visit) over 2 sequential visits that are a
- minimum of 6 weeks (target of 8 weeks) apart. If visits are not 6 weeks apart, improvement/non-
- improvement will not be evaluated until this interval is met. If the amblyopic eye VA is not
- 625 tested twice at a specific visit, improvement/non-improvement will not be evaluated until the
- next follow-up visit at which test and retest are completed.

## 4.3.2 Non-improvement of Visual Acuity ("Stable/Worsening VA")

- Non-improvement of VA is defined as no improvement in distance VA of 0.05 logMAR or more
- 630 (based on mean of test and retest) over 2 sequential visits, a minimum of 6 weeks (target of 8
- weeks) apart. If the amblyopic eye VA is not tested twice at a specific study visit,
- improvement/non-improvement will not be evaluated until the next study follow-up visit at
- which a test and retest of VA are completed.
- Non-improvement of VA ("stable/worsening") allows participants randomized to the sequential group to advance from spectacles alone (optical treatment) to added patching treatment.
- Non-improvement of VA ("stable/worsening") allows participants who have been patching in either group to be released to treatment at Investigator discretion.
- ATS22ProtocolV7.0 (24Mar2023) ATS22ProtocolV7.0 (24Mar2023)PDF

All participants will continue to return for follow-up visits every 8 weeks through 56 weeks. For participants who meet criteria of stable/worsening VA, amblyopia status is then determined in the second step in the classification (*see sections 4.3.3-7*).

## 4.3.3 Residual Amblyopia

Residual amblyopia is defined as more than 0.1 logMAR of interocular difference of distance VA between the amblyopic eye and the non-amblyopic eye (calculated for each eye as the mean of the test and retest VA measurements made at that visit).

#### 4.3.4 Resolved Amblyopia

Resolved amblyopia is defined as 0.1 logMAR or less of interocular difference of distance VA between the amblyopic eye and the non-amblyopic eye (calculated for each eye as the mean of the test and retest VA measurements made at that visit).

## 4.3.5 Stable Resolved Amblyopia

Amblyopia is defined as "stable resolved" at the study visit where the participant's amblyopia both meets the definition of non-improved ("stable/worsening") VA (*section 4.3.2*) and "resolved" amblyopia (*section 4.3.4*). NOTE: Participants cannot be considered "stable resolved" if they meet the definition for "improving" (*section 4.3.1*).

## 4.3.6 Stable Residual Amblyopia

Amblyopia is defined as "stable residual" at the study visit where the participant's amblyopia meets the definition of non-improved ("stable/worsening") VA (*section 4.3.2*) and "residual" amblyopia (*section 4.3.3*). NOTE: Participants cannot be considered "stable residual" if they meet the definition for "improving" (*section 4.3.1*).

#### 4.3.7 Amblyopia Status Examples

The following are examples of amblyopia status:

		1 VA est		1 VA test	Visit Te		, _,,_,	2 VA test	Mean Amb Eye logMAR		IOD logMAR	
Ex	Amb	Fellow	Amb	Fellow	Amb	Fellow	Amb	Fellow	Vis 1	Vis 2	Visit 2	Status
1	20/50	20/20	20/50	20/20	20/50	20/20	20/40	20/20	0.40	0.35	0.35	Improving
2	20/60	20/20	20/60	20/25	20/50	20/20	20/50	20/20	0.50	0.40	0.40	Improving
3	20/60	20/20	20/50	20/20	20/60	20/25	20/40	20/20	0.45	0.40	0.35	Improving
4	20/25	20/20	20/25	20/25	20/20	20/20	20/25	20/20	0.10	0.05	0.05	Improving
5	20/32	20/20	20/32	20/20	20/20	20/20	20/20	20/20	0.20	0.00	0.00	Improving
6	20/50	20/20	20/60	20/20	20/60	20/20	20/60	20/20	0.45	0.50	0.50	Stable residual
U	20/30	20/20	20/00	20/20	20/00	20/20	20/00	20/20	0.43	0.50	0.50	(not improving)
7	20/50	20/20	20/60	20/20	20/50	20/20	20/60	20/20	0.45	0.45	0.45	Stable residual
8	20/25	20/20	20/20	20/20	20/25	20/20	20/20	20/20	0.05	0.05	0.05	Stable resolved

## 4.3.8 Recurrent Amblyopia

Recurrent amblyopia is defined as a decrease in amblyopic eye VA of 0.2 logMAR or more and a 0.2 logMAR or more interocular difference of distance VA between the amblyopic eye and the non-amblyopic eye on a subsequent visit to the visit at which the definition of "stable resolved" was met. VA is calculated for each eye as the mean of the test and retest VA measurements

made at the visit. If VA is not tested twice at a specific visit, then the change in VA will not be evaluated until the next study follow-up visit.

Participants meeting the definition for "Recurrent amblyopia" should be treated, and the method of treatment will be at investigator discretion.

## 4.4 Study Visits

Study visits following randomization will occur at:

	Target Day	Target Window	Allowable Window
Visit	Post-Randomization	Post-Randomization*	Post-Randomization**
8 weeks	56 days	42 to 70 days	28 to 83 days
16 weeks	112 days	98 to 126 days	84 to 139 days
24 weeks	168 days	154 to 182 days	140 to 195 days
32 weeks	224 days	210 to 238 days	196 to 251 days
40 weeks	280 days	266 to 294 days	252 to 307 days
48 weeks	336 days	322 to 350 days	308 to 363 days
56 weeks	392 days	378 to 406 days	364 to 504 days

\* Target window is target day  $\pm 2$  weeks.

A text message will be sent by the Coordinating Center to remind the participant and family of the next study visit for participants who consent to receive text messages during the study.

Parents will be asked to complete a daily compliance calendar by recording how long the patch was worn each day (if applicable) and/or how long the child wore his/her spectacles each day.

If visits are not at least 6 weeks apart, improvement/non-improvement will not be evaluated until the participant has 2 visits at least 6 weeks apart. If VA is not tested twice at a specific study visit, the change in VA will not be evaluated until the next study follow-up visit.

Participants who (because of unforeseen circumstances) are unable or unwilling to return for all study follow-up visits will be permitted to return for the 56-week final visit *only* as an alternative to withdrawal from the study.

Additional office visits may occur as needed, however VA results from these non-study office visits will not be used for determination of VA stability.

\* Allowable window is (target day -4 weeks) to (target day +4 weeks minus 1 day); except for 56-week visit which is (target day -4 weeks) to (target day +16 weeks).

## 4.4.1 Testing Procedures at Study Visits

The following procedures will be performed in the following order in **current spectacle correction** in both groups at each visit, unless otherwise specified. A Masked Examiner must complete distance VA testing at visits prior to and at time of primary outcome (*section 4.4.1*). If a participant currently wears spectacles but is not wearing them at the follow-up examination for whatever reason, testing must be performed in trial frames using the last spectacle prescription. Prior to the Masked Examiner entering the room, participants and parents should be instructed not to discuss their assigned treatment with the Masked Examiner. Prior to performing any testing, the participant's spectacle correction will be verified using a lensometer. Spectacles should meet the following tolerances compared with the last cycloplegic refraction:

- Sphere power must be within 0.25 D of the prescribed correction.
- Cylinder power must be within 0.25 D of the prescribed correction.
- Axis must be within +/- 10 degrees if cylinder power is ≤1.00D, and within +/- 5 degrees if cylinder power is >1.00D.

If spectacles do not meet these tolerances, the participant should be tested with trial frames using the last spectacle prescription.

The PedEyeQ child questionnaire (or proxy questionnaire) and parent questionnaire should be completed before any clinical testing.

For more details, see the ATS Procedures Manual:

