#### 1. PedEyeQ:

• The PedEyeQ is a patient-derived questionnaire designed to assess functional vision and eye-related quality of life. It consists of a child questionnaire for children ages 5 years and older, a proxy questionnaire completed by the parent regarding their child, and a parent questionnaire regarding the parent's own quality of life. The child questionnaire is administered by study personnel to children under the age of 8 years and is completed by the child for children 8 years of age or older (with the help of study personnel, if needed). Proxy and Parent questionnaires are completed by the parent. The questionnaires take about 10 minutes to complete.

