# 2. Distance VA Testing (performed by a **masked** examiner prior to and at time of Primary Outcome):

 Monocular distance VA testing will be performed in the participant's current spectacle correction in each eye by a masked certified examiner using the electronic ATS-HOTV VA protocol for children <7 years and the E-ETDRS VA protocol for children ≥ 7 years on a study-certified acuity tester displaying single surrounded optotypes.

• The same VA protocol used at enrollment will be used throughout the study regardless of age at follow-up

- Repeat Distance VA Testing (performed by a masked examiner prior to and at time of Primary Outcome): Monocular distance VA testing will be performed in current refractive correction in each eye by a masked certified examiner (as above).
  - 4. Binocularity Testing (may be performed by an unmasked examiner)
    - Gross binocularity will be tested in current spectacle correction at near using the hand-held Worth 4-Shape test held at 40 cm.
    - Stereoacuity will be tested at near in current spectacle correction using both the Randot Butterfly and Randot Preschool stereoacuity tests.
  - 5. Ocular Alignment Testing (may be performed by an unmasked examiner)
    - Ocular alignment will be assessed in the current spectacle correction by the cover test, simultaneous prism and cover test (SPCT) (in cases of strabismus detected by cover test), and prism and alternate cover test (PACT) in primary gaze at distance (3 meters) and at near (1/3 meter).
  - 6. Contrast Sensitivity Testing (only at the time of the Primary Outcome visit; May be performed by an unmasked examiner)
    - Contrast sensitivity will be assessed in the current spectacle correction in each eye (right eye first then left eye) using the SpotChecks™ Contrast Sensitivity Test. Testing will be repeated in the left eye at the 8-week post-randomization visit, until there is sufficient sample size to perform test-retest reliability analysis.
  - 7. Adherence Monitoring: Adherence data from the ODM will be downloaded and compliance calendars will be reviewed.

The following additional testing is performed at the end of the visit when required as defined below in section 4.4.1.1.:

8. Cycloplegic Refraction (at the time of the Primary Outcome visit, if required by 4.4.1.1)

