## **6.2** Definition of Participant Cohorts

880 881 Two cohorts of participants with identical eligibility criteria, apart from age at time of randomization will be enrolled:

882 883

- Children aged 3 to <7 years at randomization referred to as the 'younger cohort'
- 884

• Children aged 7 to <13 years at randomization referred to as the 'older cohort'

885 886

887 888

889

890

891

892

Overall response to amblyopia treatment has been found to be somewhat reduced in children 7 years and older and it is likely that there are differences in adherence with spectacle correction and with prescribed patching between children <7 years and children 7 years and older; therefore, we believe that there could be a differential treatment effect between the two age cohorts. Recruitment potential is also expected to differ between the two age cohorts given the requirement for no prior treatment for amblyopia. Therefore, statistical considerations are different for the two age cohorts and all analyses described below will be conducted separately within each age cohort.

893 894

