## **6.5** Secondary Efficacy Outcomes

All secondary outcomes involving amblyopic eye distance VA will use the ITT dataset with amblyopic eye distance VA imputed when missing. Secondary outcomes not involving amblyopic eye distance VA will use observed data, with no imputation for missing data.

For secondary outcome comparisons that are based on a parametric statistical model, all model assumptions will be checked, and if violated, data transformation or a non-parametric alternative will be used instead.

	JAEB CENTER FOR HEALTH RESEARCH
964	The distribution of all secondary outcomes will be tabulated at randomization and the outcome
965	visit for each randomized treatment group and described using descriptive statistics.
966	
967	Treatment group comparisons on secondary clinical outcomes will be controlled using the false
968	discovery rate (FDR) method at 5% and to adjust p-values and confidence intervals for
969	multiplicity.
970	
971	6.5.1 Pediatric Eye Questionnaire (PedEyeQ)
972	Rasch scores for each questionnaire item will be obtained from published look-up tables
973	available at www.pedig.net, and used to calculate a score for each participant and a separate
974	treatment group mean for each of the PedEyeQ domains of the Child, Proxy, and Parent
975	PedEyeQ at randomization and at each visit. Scores will also be converted to a 0-100 scale to
976	aid in interpretation.

976 977

978

979

980 981

982

983 984

985

986

987

988

989 990

991

992

- Child PedEyeQ:
  - Functional Vision
    - o Bothered by Eyes and Vision
  - Social
  - o Frustration / Worry
- Proxy PedEyeQ:
  - Functional Vision
  - o Bothered by Eyes and Vision
  - o Social
  - o Frustration / Worry
  - o Eye care
- Parent PedEyeO:
  - o Impact on Parent and Family
  - Worry about Child's Eye Condition
  - Worry about Self-perception and Interactions
  - Worry about Functional Vision

993 994 995

996 997

998

999

1000 1001

1002

Comparisons of interest, following the hypotheses detailed in the Background section are as follows:

- Comparison of domain scores between treatment groups at 8 weeks (the first follow-up visit, before the sequential group has the opportunity to start patching and is still in spectacle correction).
- Comparison of domain scores between treatment groups at the primary outcome visit defined as in *section 6.4*.
- Comparison of domain scores between treatment groups at the conclusion of the study (56 weeks).

1003 1004 1005

1006

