Mean Rasch scores for each domain will be compared between randomized treatment groups using linear models, adjusting for baseline domain score and other baseline factors known to be associated with health-related quality of life (HRQOL).

All analyses will test the null hypothesis of no difference between treatment groups. The false discovery rate (FDR) method will be used to control the FDR at 5% and to adjust p-values and confidence intervals for multiplicity.

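### The Child PedEyeQ starts at age 5, so children who turn 5 during follow-up can have a 56-week Child score that the stated baseline-adjusted model cannot use, and the child-or-proxy wording contradicts the analysis

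*Protocol*

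**What the plan says.** - **Who completes what.** Section 3.1.3 (item 1) and section 4.4.1 (item 1) describe the PedEyeQ in the same terms: "It consists of a child questionnaire for children ages 5 years and older", a proxy form completed by the parent about the child, and a parent form. Only the Child form has an age limit.
- **Procedure sentence.** Sections 3.1.1 and 4.4.1 both carry the line "The PedEyeQ child questionnaire (or proxy questionnaire) and parent questionnaire should be" completed before clinical tests.
- **When.** The section 4.4.1 procedures are done "in both groups at each visit, unless otherwise specified". Section 4.4 sets the 56-week visit at day 392, with an allowable window of "364 to 504 days".
- **Who is studied.** Section 6.2: "Children aged 3 to <7 years at randomization referred to as the 'younger cohort". Section 6.12.4 plans 272 children in this cohort.
- **Analysis.** Section 6.5.1 calls for Child, Proxy and Parent domain scores at randomization and at each visit. It compares the arms at 8 weeks, the primary outcome visit and 56 weeks with linear models "adjusting for baseline domain score and other baseline factors". Under section 6.5, secondary outcomes other than amblyopic-eye VA "will use observed data, with no imputation for missing data".
- **Contrast with VA.** Section 4.4.1 (item 2): "The same VA protocol used at enrollment will be used throughout the study regardless" of the child's later age. No comparable rule is given for the PedEyeQ.

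**The concern.** Two problems meet at the fifth birthday.

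First, a child under 5 at randomization cannot supply a Child baseline, but may be old enough for the Child form later. A model that needs the baseline domain score, fitted to observed data without imputation, has no place for that child's follow-up score. The protocol dealt with age-crossing for VA by fixing the test at enrollment, and is silent for the PedEyeQ.

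Second, the procedure sentence can be read as a choice between the Child and Proxy forms, while section 6.5.1 analyses both sets of domains. A site that takes the choice literally would give no Proxy form once the child is 5. Scores never collected cannot be recovered at analysis.

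Child and parent quality of life is the trial's second stated question if VA proves equivalent (section 1.5), and 56 weeks is one of three named comparison times.

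**Working it through.** **Inputs from the protocol.** Child form from age 5 (sections 3.1.3 and 4.4.1); cohort 3 to under 7 years (6.2); n = 272 (6.12.4); 8-week visit at day 56, 56-week visit at day 392 with window 364 to 504 (4.4).

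**Input not in the protocol.** The age distribution within the cohort. It is assumed uniform, then varied.

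**The plan's own figure.** With margin 0.75 lines, SD 1.7, true difference 0, one-sided alpha 0.025 and 90% power for two one-sided tests, n per arm = 2 × 1.7² × (1.960 + 1.645)² / 0.75² ≈ 134. With the t distribution, 136 per arm gives 90.4% power. The 272 is confirmed, and it serves here only as a head count.

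**Formula.** Let t = day / 365.25. A child has a Child score at that day if baseline age is at least 5 − t, and a Child baseline only if baseline age is at least 5. The share of Child scores without a baseline is P(5 − t ≤ age < 5) / P(age ≥ 5 − t).

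**Uniform ages, 56 weeks.**
- t = 392 / 365.25 = 1.073 years, so the affected ages are about 3.93 to under 5.
- Turning 5 on study: 1.073 / 4 = 26.8%, about 73 of 272.
- Child baseline available: 2 / 4 = 50%, or 136.
- Child score at 56 weeks: 3.073 / 4 = 76.8%, about 209.
- Share without a baseline: 73 / 209 = 34.9%.
- Across the window: 0.997 / 2.997 = 33% at day 364, and 1.380 / 3.380 = 41% at day 504.

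**Uniform ages, 8 weeks.** t = 56 / 365.25 = 0.153, and 0.153 / 2.153 = 7.1%, about 10 of 146 Child scores.

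**Other assumed age mixes, day 392.**

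| Assumed ages | Share without a baseline |
|---|---|
| 10/20/35/35% aged 3/4/5/6 | 23% |
| 15/25/35/25% | 30% |
| 25/30/25/20% | 41% |
| Truncated normal, mean 5, SD 1.1 | 42% |
| Truncated normal, mean 4.5, SD 0.9 | 61% |

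**Cost in precision.** Under uniform ages, analysing 136 instead of 209 children multiplies the standard error by √(209 / 136) = 1.24, ignoring what baseline adjustment gains. These counts are before dropout. The 10% loss in section 6.12.4 is expected to be equal between arms. If it is also unrelated to age, the fractions do not change.

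**The procedure sentence.** This needs no age assumption. Sections 3.1.1 and 4.4.1 offer the Child form or the Proxy form. The item descriptions in sections 3.1.3 and 4.4.1 list Child, Proxy and Parent forms, with no age limit on the Proxy form. Section 6.5.1 analyses Child and Proxy domains separately. The sentence and the analysis cannot both be followed for a child of 5 or older.

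**The case against.** The strongest reply has four parts.

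**The switch at age 5 is not stated.** The age limit appears in a description of the instrument, and details are left to a procedures manual that is not at hand. This stands as a qualification. Visit age is the natural reading, because the description is repeated for follow-up visits and only the VA test is fixed at enrollment. If the form is instead fixed by baseline age, no scores are dropped, but the Child comparison then covers only children aged 5 or older at randomization (136 of 272 under uniform ages). A stated rule is needed either way.

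**A missing covariate is usually a matter for the SAP.** Section 6.1 calls the methods a summary, and the no-imputation rule speaks of outcomes. An SAP could add a rule. But the protocol itself fixes both the baseline covariate and observed-data analysis, and together, as written, they leave these scores out.

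**The Proxy form already bridges the fifth birthday.** It has no age limit and covers all four Child domains plus eye care. This stands, provided the Proxy form is given to everyone, which is why the procedure sentence matters. That sentence mainly sets the order of testing, and its choice of forms may be meant for children under 5.

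**The arms are not distorted.** This also stands. Whether a child has a baseline depends on age before randomization, so the loss should be similar in both arms.

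A reader might therefore infer too much: that a third of scores will certainly be lost, that the treatment comparison is biased, or that Proxy data are already compromised. The documents support none of these. They give no age distribution, the missingness precedes randomization, and Proxy scores are lost only where a site reads the choice literally.

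**Conclusion.** The point holds in a limited form. With the age limit applied at each visit, the stated model cannot use the 56-week Child scores of children aged about 3.93 to under 5 at randomization. Under assumed uniform ages that is about 35% of those scores, with a range of about 23% to 61% over other assumed mixes; at 8 weeks it is about 7% under uniform ages. No figure is offered for the primary outcome visit, which can fall well before 56 weeks.

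The effect is lost precision (standard error up to about 1.24 times larger under uniform ages) and a Child comparison resting on older children. It is confined to Child domains in the younger cohort. The primary VA analysis, the sample size, the Parent domains and the older cohort's Child domains are unaffected.

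The procedure sentence is a separate contradiction. Read literally, it would lose Proxy scores for children aged 5 or older. Both matters should be corrected, but neither threatens the trial's main conclusion.

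**What to change.** 1. **Sections 3.1.1 and 4.4.1.** Replace the child-or-proxy sentence with a statement that the Proxy and Parent forms are completed for all children at every visit, plus the Child form for children aged 5 or older at that visit.
2. **Section 6.5.1, 8-week and 56-week comparisons.** Keep children who have a Child follow-up score but no Child baseline, using a missing-baseline indicator together with baseline age. Both are fixed before randomization. Report the subset aged 5 or older at randomization as a sensitivity analysis.
3. **Section 6.5.1, primary outcome visit.** Make the subset aged 5 or older at randomization the main Child-domain analysis. The timing of this visit can differ by arm: under section 6.4 the sequential group can reach stable residual status only after patching has begun. Who has turned 5 by then could therefore depend on treatment, and the indicator should not be used there as the main approach.

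The cost is one sentence in each of two procedure sections and a short analysis rule. At sites that now read the sentence as a choice, the parent also completes the Proxy form, within the roughly 10 minutes the protocol already allows for the questionnaires.
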